5.1.2 Bone Marrow Biopsy

A bone marrow biopsy will be performed at screening unless an archived sample is available at the time of screening:

- Patients with bone marrow biopsies demonstrating lymphoma within 12 months are not required to undergo a repeat bone marrow evaluation prior to study entry.
- Patients with a prior bone marrow biopsy negative for lymphoma, or with no bone marrow biopsy, will be required to undergo restaging marrow biopsy within 60 days prior to randomization.
- From Week 12 until EOS, a second bone marrow biopsy is required only if initially positive and to confirm CR based on the investigator's review of CT scan.

5.1.3 Histopathological Review of Diagnostic Tissue

To be eligible for this study, patients must have tumor tissue or slides available for review by a central pathology review committee. If a biopsy has not been performed within the previous 24 months prior to screening visit, a new biopsy is required to confirm that the histology is unchanged. At screening, the diagnosis will be based on histopathological review by the enrolling institution. Tumor tissue blocks or slides will be collected and sent to the central laboratory for retrospective standardized evaluation of the diagnosis of Grade 1-3a, CD20+ follicular lymphoma containing no elements of diffuse large B-cell lymphoma.

5.2 Safety

5.2.1 Adverse Events

Assessment of AEs will include type, incidence, severity (graded by NCI-CTCAE version 4.03), timing, seriousness, and relatedness. (Section 6)

5.2.2 Physical Examination

A physical examination will be performed by the Investigator and recorded as ‘normal’ or ‘abnormal’ with specified abnormalities at the visits indicated in Table 1. Any persisting abnormalities should be stated each time the examination is performed. Diagnosis of new abnormalities, or worsening of abnormalities, should be recorded as AEs, if appropriate.

Whenever possible, the same person at each study site should perform the physical examination throughout the study. The physical examination should include assessment of general appearance, skin, head, neck, throat, thyroid, abdomen, cardiovascular, neurological, musculoskeletal/extremities, and respiratory systems, as appropriate, and consistent with local standard of care. Lymph nodes, spleen and liver should be included at all times. Any specific signs or symptoms that are medically significant should be reported. Particular attention should be paid to any new or worsening neurological symptoms or signs that may be suggestive of PML (typical symptoms are diverse and include cognitive or visual disorders, hemiparesis, confusion and behavioral disorders).

Body weight will also be measured. Height will be measured at screening (Visit 1) only.

5.2.3 Vital Signs

Vital signs will be assessed at the visits indicated in Table 1. Measurements will include systolic and diastolic blood pressure, pulse, respiratory rate, and oral or tympanic body temperature, and should be performed after the patient has been in a sitting/lying down position for at least 5 minutes.

During all infusions of the study drug, vital signs will be assessed at the following times:

1. Pre-infusion (within 10 minutes prior to the start of the infusion).
2. Start of infusion (within 30 minutes after the start of the infusion).
3. End of infusion (within 10 minutes after the end of the infusion).

Additional readings may be assessed at the discretion of the Investigator in the event of an infusion-related reaction.

The Investigator must assess all vital signs findings at each visit. If the Investigator finds any clinically relevant abnormalities, these should be reported as AEs/SAEs as appropriate.

5.2.4 ECOG Performance Status

ECOG performance status will be graded according to the definition in Appendix 6.

5.2.5 Clinical Laboratory Evaluations

A list of clinical laboratory assessments to be measured is provided in Table 2. Additional parameters may be measured in the event of AEs, and as necessary for patient care.

If any laboratory findings meet the definition of hepatic injury (see Appendix 9), patients should be managed according to the instructions in Appendix 9.

Blood and urine samples will be collected at the times indicated in Table 1.

Table 2 Clinical Laboratory Assessments

Hematology	Hemoglobin, hematocrit, platelets, white blood cells with differentiation, and neutrophils (absolute counts)
Clinical chemistry (serum)	Creatinine, alkaline phosphatase, total bilirubin, AST, ALT, total protein, albumin, calcium, BUN, phosphorus, uric acid, and electrolytes (sodium, potassium, chloride)
Urinalysis	Glucose, protein, blood, and leukocytes
Virology	Hepatitis C virus antibodies, human immunodeficiency virus, hepatitis B surface antigen, hepatitis B core antibody (total and immunoglobulin M), and HBV DNA
Pregnancy testing	hCG (serum or urine, as appropriate)
Tumor markers (serum)	β 2 microglobulin and LDH

Note: Additional parameters may be measured in the event of AEs, and as necessary for patient care.
 ALT alanine aminotransferase; AST aspartate aminotransferase; BUN blood urea nitrogen;
 HBV DNA hepatitis B virus deoxyribonucleic acid; hCG human chorionic gonadotropin;
 LDH lactate dehydrogenase

It is the responsibility of the Investigator or Sub-investigator to review the results of all laboratory tests as they become available. For each abnormal laboratory test result, the Investigator or Sub-investigator needs to ascertain if this is an abnormal (i.e., clinically significant) change from baseline for that individual patient. This determination, however, does not necessarily need to be made the first time an abnormal value is observed. The Investigator or Sub-investigator may repeat the laboratory test or conduct additional tests to verify the results of the original clinical laboratory tests. If this laboratory value is determined by the Investigator or Sub-investigator to be a clinically significant change from baseline for that patient, it is considered to be an AE (Section 6.7).

Blood samples for laboratory safety tests will be analyzed locally according to local practice and local regulatory guidance. Tuberculosis status will be determined using tuberculosis skin test (e.g. Mantoux test) or interferon-gamma release assay (IGRA e.g. the QuantiFERON-TB Gold Assay). TB testing is required only if it is required by local regulation or at the investigator's discretion.

Detailed sample collection, labeling, storage, and shipment information will be described in the Laboratory Manual.

5.2.6 Electrocardiogram

Resting 12-lead ECG data will be collected at the visits indicated in Table 1.

Patients should rest for at least 5 minutes in a supine position before the ECG evaluation.

The original ECG traces and variables must be stored in the patients' medical record as source data. The Investigator should evaluate the ECG from a clinical perspective and the result (whether the ECG result is normal or abnormal) should be recorded on the ECG tracing and on the appropriate section of the eCRF. Any clinically relevant abnormalities will be reported as AEs/SAEs as appropriate. Further ECGs should be performed at the Investigator's discretion.

5.2.7 Pregnancy

A serum pregnancy test will be performed at screening, at Week 28, Week 52 (EOS) and urine pregnancy test will be performed on Day 1 prior to dosing indicated in Table 1 to rule out pregnancy in female patients of childbearing potential. Additional tests may also be undertaken by local regulations.

Any pregnancy in a female patient should be reported to the Sponsor from the time the patient signed the ICF until 12 months after the last infusion of study drug. Pregnancy reports should be submitted to the Sponsor within 24 hours of awareness of the pregnancy by the Investigator as per the reporting procedure outlined in the Site Manual.

Pregnancy occurring in the partner of a male patient participating in the study should be reported to the Investigator and the Sponsor following the same procedure for pregnancy in the female patient. The partner should be counseled, the risks of continuing the pregnancy discussed, as well as the possible effects on the fetus. Monitoring of the pregnant female should continue until conclusion of the pregnancy. The pregnant partner will need to sign an Authorization for "Use and Disclosure of Pregnancy Health Information" (a sort of specific consent form) to allow for follow-up of her pregnancy.

Although pregnancy is not an AE, all pregnancies must be followed until 6 to 8 weeks after the estimated date of delivery to determine their outcome including the information of fetus/new-born. The pregnancy outcome will be notified to the Sponsor by submitting a follow-up pregnancy report form. If the outcome of the pregnancy meets the SAE criteria, then the Investigator should report this case according to the SAE reporting process (Section 6.9).

5.2.8 Safety Monitoring

An independent DSMB, consisting of members who are independent from the Sponsor, the contract research organization (CRO) and the study, will be established to act in an advisory capacity to monitor patient data. The DSMB will review available study data at pre-specified time points, as outlined in the DSMB charter.

The details of the DSMB roles and responsibilities, the stopping rules for safety reasons, and the logistics of the DSMB activities will be outlined in a DSMB charter.

5.3 Immunogenicity Assessments

Determination of the incidence of HACA and neutralizing antibody will be performed by central laboratory using validated analytical methods. Blood samples (approximately 5 to 8 mL) will be taken at the visits shown in Table 1. Immunogenicity assessment is also planned when patients show signs or symptoms of immune-response-related adverse events including anaphylaxis (Section [6.4.3](#)) and mucocutaneous reaction (Section [6.4.5](#)). The exact date/time of the blood sample collection will be recorded in the patient's eCRF. Wherever possible, immunogenicity blood samples will be taken at the same time as blood is drawn for other analyses to limit repeated venipuncture.

Approximately 80 mL of whole blood will be obtained from each patient for immunogenicity assessments during the study.

Human anti-chimeric antibody will be detected in serum samples using validated analytical methods. Serum samples in which HACA are detected will be reflexed to a Neutralizing Antibody Assay to evaluate the effect of the HACA on the biological activity of rituximab.

Full instructions for collection, labeling, storage, and shipment of samples are provided in the Laboratory Manual.

5.4 Pharmacokinetic Assessments

Blood samples for the determination of concentrations of rituximab will be taken at the times specified in the schedule of assessments (Table 1).

Individual venipunctures for each time point may be performed, or an indwelling catheter may be used. The exact date/time of the blood sample collection will be recorded in the patient's eCRF.

The blood samples (approximately 5 mL) will be drawn and processed using instructions provided by the designated central laboratory. Serum (approximately 2.5 mL) will be harvested and evenly divided into 2 samples (duplicates) to allow for a back-up sample.

Approximately 60 mL of whole blood will be obtained from each patient for PK assessments during the study.

Determination of serum concentrations of rituximab will be performed by central laboratory using validated analytical methods. Detailed sample collection, labeling, storage, and shipment information will be described in the Laboratory Manual.

5.5 Pharmacodynamic Assessments

Blood samples for the determination of CD19+ count will be taken at the times specified in the schedule of assessments (Table 1). The exact date/time of the blood sample collection will be recorded in the patient's eCRF.

The blood samples (approximately 5 mL) will be drawn and processed using instructions provided by the designated central laboratory.

Approximately 70 mL of whole blood will be obtained from each patient for PD assessments during the study.

Because rituximab depletes B-cells, circulating levels of IgG and IgM may decrease. Blood samples for IgG and IgM will be collected according to the schedule of assessments (Table 1).

The blood samples will be analyzed for CD19+ count by designated central laboratory using validated analytical methods. Detailed sample collection, labelling, storage, and shipment information will be described in the Laboratory Manual.

6.0 REPORTING OF ADVERSE EVENTS

6.1 Adverse Events

Definition of AE: An AE is any untoward medical occurrence in a subject or clinical investigation subject administered a pharmaceutical product and which does not necessarily have a causal relationship with this treatment.

An AE can therefore be any unfavorable and unintended sign (including an abnormal laboratory finding, for example), symptom, or disease temporally associated with the use of a medicinal product, whether or not considered related to the medicinal product.

6.2 Serious Adverse Events

A SAE is any untoward medical occurrence (whether considered to be related to study drug or not) that at any dose:

- Results in death.
- Is life-threatening. The term “life-threatening event” refers to an event in which the subject was at risk of death at the time of the event; it does not refer to an event which hypothetically might have caused death if it were more severe.
- Requires inpatient hospitalization or prolongation of existing hospitalization: Hospital admissions and/or surgical operations planned before or during a study are not considered AEs if the illness or disease existed before the subject was enrolled in the study, provided that it did not deteriorate in an unexpected way during the study. Hospitalizations required purely for the purposes of performing study procedures are not SAEs.
- Results in persistent or significant disability/incapacity.
- Is a congenital abnormality/birth defect, which includes ectopic pregnancy, spontaneous abortion, intrauterine fetal demise, or neonatal death. In addition, infant death within 1 month of birth should be reported as a SAE when the investigator assesses the infant death as related or possibly related to exposure to investigational product.
- Any other medically significant event that, although it may not be immediately life-threatening or result in death or hospitalization, endangers the subject or requires that appropriate measures be taken to avoid any of the events listed above (e.g., bronchospasm requiring intensive treatment, blood dyscrasia or convulsion not

requiring hospitalization, drug dependency, or abuse). Subjects may be hospitalized for observation at the discretion of the Investigator; such instances of hospitalization will not be recorded as SAEs.

6.3 Adverse Drug Reactions

An adverse drug reaction (ADR) is defined as a noxious and unintended response to a medicinal product related to any dose.

AEs which meet all of the following criteria:

- Serious
- Unexpected (i.e. is not consistent with the currently applicable Investigator Brochure list of AEs)
- There is at least a reasonable possibility that there is a causal relationship between the event and the medicinal product

will be classified as Suspected Unexpected Serious Adverse Reactions (SUSARs) and should be reported to the relevant ethics committee and to the relevant Health Authorities for expedited reporting in accordance with Directive 2001/20/EC or as per national regulatory requirements in participating countries.

6.4 Adverse Events of Special Interest

An AE of special interest (AESI) is one of scientific and medical interest specific to understanding of the study drug and may require close monitoring and rapid communication by the Investigator to QuintilesIMS. An AESI may be serious or non-serious. The rapid reporting of AESIs allows ongoing surveillance of these events in order to characterize and understand them in association with the use of this study drug. All AESIs must be reported in an expedited manner similar to SAEs (i.e., non-serious AESIs also must follow serious timelines).

The following will be considered AESIs in this study: progressive multifocal leukoencephalopathy (PML), hepatitis reactivation, infusion reactions, anaphylactic reactions, mucocutaneous reactions and serious infections.

6.4.1 Progressive Multifocal Leukoencephalopathy

The Investigator is required to monitor the patients throughout the study for any new or worsening neurological symptoms or signs that may be suggestive of PML. Typical symptoms are diverse, and include cognitive or visual disorders, hemiparesis, confusion, and

behavioral disorders. If a patient develops new or worsening neurological signs or symptoms, he/she will be evaluated for PML. Neurological warning signs include:

- Major changes in vision, unusual eye movements;
- Loss of balance or coordination;
- Disorientation or confusion.

If PML is suspected, further dosing must be suspended until PML has been excluded.

Consultation with a neurologist should be considered as clinically indicated. If any doubt exists, further evaluation, including an MRI scan (preferably with contrast), cerebrospinal fluid testing for John Cunningham viral deoxyribonucleic acid (DNA), and repeat neurological assessments, should be considered.

If any patient is diagnosed of PML during the study, the patient must be discontinued and followed up until resolution at the discretion of the Investigator.

6.4.2 Hepatitis Reactivation

If a patient develops reactivation of HBV while on rituximab, the patient should be managed as outlined in Section 4.11.3.

6.4.3 Anaphylactic Reactions

Anaphylaxis is a serious allergic reaction that is rapid in onset and may cause death. Diagnostic criteria are outlined in Table 3.

Table 3 Clinical Criteria for Diagnosing Anaphylaxis

Anaphylaxis is highly likely when any one of the following 3 criteria are fulfilled:	
1.	Acute onset of an illness (minutes to several hours) with involvement of the skin, mucosal tissue, or both (eg, generalized hives, pruritus, or flushing, swollen lips/tongue/uvula) AND AT LEAST ONE OF THE FOLLOWING a. Respiratory compromise (e.g., dyspnea, wheeze/bronchospasm, stridor, reduced peak expiratory flow (PEF), hypoxemia) b. Reduced blood pressure or associated symptoms of end-organ dysfunction (e.g., hypotonia [collapse], syncope, incontinence)
2.	Two or more of the following that occur rapidly after exposure to a likely allergen for that subject (minutes to several hours): a. Involvement of the skin/mucosal tissue (e.g., generalized hives, itch/flush, swollen lips/tongue/uvula) b. Respiratory compromise (e.g., dyspnea, wheeze/bronchospasm, stridor, reduced PEF, hypoxemia) c. Reduced blood pressure or associated symptoms (e.g., hypotonia [collapse], syncope, incontinence) d. Persistent gastrointestinal symptoms (e.g., crampy abdominal pain, vomiting)
3.	Reduced blood pressure after exposure to known allergen for that subject (minutes to several hours): a. Infants and children: low systolic blood pressure (age specific) or greater than 30% decrease in systolic blood pressure b. Adults: systolic blood pressure of less than 90 mm Hg or greater than 30% decrease from that person's baseline

As with the treatment of any critically ill patient, the treatment of anaphylaxis begins with a rapid assessment and maintenance of airway, breathing, and circulation. When a patient fulfills any of the 3 criteria of anaphylaxis outlined in Table 3, the patient should receive epinephrine immediately (the treatment of choice in anaphylaxis). There undoubtedly will be patients who present with symptoms not yet fulfilling the criteria of anaphylaxis yet in whom it would be appropriate to initiate therapy with epinephrine, such as a patient with a history of near-fatal anaphylaxis to peanuts who ingested peanuts and within minutes is experiencing urticaria and generalized flushing. Subsequent interventions are determined on the basis of the clinical course and response to epinephrine. Additional immunogenicity sampling is required in this case.

6.4.4 Serious Infections

Serious infections are defined as infections requiring i.v. antibiotics or meeting the definition of a SAE.

6.4.5 Mucocutaneous Reactions

Mucocutaneous reactions, some with fatal outcome, can occur in patients treated with rituximab. These reactions include paraneoplastic pemphigus, Stevens-Johnson syndrome, lichenoid dermatitis, vesiculobullous dermatitis, and toxic epidermal necrolysis. The onset of these reactions has been variable and includes reports with onset on the first day of rituximab exposure. Rituximab should be discontinued in patients who experience a severe mucocutaneous reaction. The safety of re-administration of rituximab to patients with severe mucocutaneous reactions has not been determined. Additional immunogenicity sampling is required in this case.

6.4.6 Infusion Reactions

An acute onset infusion reaction generally occurs within 24 hours of infusion of the study drug. Rituximab can cause severe, including fatal, infusion reactions. Severe reactions typically occur during the first infusion with time to onset of 30 to 120 minutes. Rituximab-induced infusion reactions and sequelae include headache, nausea, fever or chills, dizziness, flush, urticaria, hypotension, angioedema, hypoxia, bronchospasm, pulmonary infiltrates, acute respiratory distress syndrome, myocardial infarction, chest or back pain, ventricular fibrillation, cardiogenic shock, anaphylactoid events, or death. Distinction between infusion reaction and anaphylaxis is necessary.

Medical management (e.g., glucocorticoids, epinephrine, bronchodilators, or oxygen) for infusion reactions must be instituted as needed. Depending on the severity of the infusion reaction and the required interventions, rituximab may be temporarily or permanently discontinued. If the same severe (Grade 3) or above infusion reaction occurs for a second time, the decision to discontinue permanently should be seriously considered. Resume infusion at a minimum 50% reduction in rate after symptoms have resolved (see Appendix 8). Closely monitor patients with pre-existing cardiac or pulmonary conditions.

.Please refer also to Section 6.4.3 (Anaphylactic Reactions) for differential diagnosis with anaphylaxis.

6.5 Adverse Events Due to Malignancy

Progression of FL (underlying disease) and death due to progression of FL are considered as outcome events and are exempted from reporting as SAEs. These outcome events will be collected and monitored by the DSMB.

However, when there is evidence suggesting a causal relationship between study drug and the progression of underlying malignancy, the event must immediately be reported as a SAE. Progression due to the usual disease evolution (or lack of efficacy of study drug) should not

be reported as SAE. Cancers with new histology should always be reported as serious adverse event.

Please refer to definition of progression that warrants initiation of treatment chemotherapy/radiotherapy in Appendix 11.

6.6 Overdose

An overdose of SAI101 or MabThera[®] is defined as an infusion of >1,000 mg during a single infusion in this study.

In case of overdose, the patient must be managed for any AE caused by the overdose as per the standard of care at the site, or symptomatically, and the case discussed with QuintilesIMS' and the Sponsor's medical advisors for decision on discontinuation of the patient.

When an overdose is reported during the course of the study, the patient should be monitored closely and evaluated by the Investigator to determine whether the patient experiences any AE or SAE as a result of the overdose.

Overdoses will be reported as protocol deviations. If the overdose is associated with an AE/SAE, the site should follow the AE/SAE reporting procedures described in Section 6.8 of this protocol.

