3.2.2 Exclusion Criteria

Patients will not be entered in the study for any of the following reasons:

1. Previous treatment with any chemotherapy and/or rituximab or other monoclonal antibody.
2. Prior radiotherapy completed <28 days before study enrollment.
3. Anticipated need for concomitant administration of any other experimental drug, or a concomitant chemotherapy, anticancer hormonal therapy, radiotherapy, or immunotherapy during study participation.
4. Concomitant disease which requires continuous therapy with corticosteroids at doses equivalent to prednisolone >20 mg/day.
5. Leukemia or transformation to diffuse large B cell lymphoma secondary to previously untreated follicular lymphoma.

6. Prior or concomitant malignancies within 5 years prior to screening, with the exceptions of non-melanoma skin cancer, adequately treated carcinoma in situ of the cervix, adequately treated breast cancer in situ, and localized prostate cancer stage T1c, provided that the patient underwent curative treatment and remains relapse free.
7. Patients with a body surface area $>3.0 \text{ m}^2$.
8. Major surgery (excluding lymph node biopsy) within 28 days prior to randomization.
9. Primary or secondary immunodeficiency (history of, or currently active), including known history of human immunodeficiency virus (HIV) infection or positive test at screening.
10. Acute, severe infection (e.g., sepsis and opportunistic infections), or active, chronic or persistent infection that might worsen with immunosuppressive treatment (e.g., herpes zoster).
11. Positive serological test for hepatitis B surface antigen (HBsAg), hepatitis B core antibody (HBcAb) or hepatitis C serology.
 - Patients with a negative HBsAg and positive HBcAb must have a hepatitis B virus (HBV) deoxyribonucleic acid (DNA) level $<20 \text{ IU/mL}$ (or 112 copies/mL) by polymerase chain reaction (PCR). These HBV patients must be willing to undergo PCR HBV DNA testing during study and may participate following consultation with a hepatitis expert regarding monitoring and use of HBV antiviral therapy, and provided that they agree to receive treatment as indicated. An HBV re-test will be performed at each study visit from Week 5 onwards, and at the discretion of the Investigator.
 - Patients with a positive test because of HBV vaccine may be included (i.e., anti-HBs+, anti-HBc-).
 - Patients positive for hepatitis C virus (HCV) antibody are eligible only if PCR is negative for HCV ribonucleic acid (RNA).

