4.2 Formulation and Packaging

SAIT101 and MabThera[®] will be provided in sterile, preservative-free, non-pyrogenic, single-use vials containing 500 mg of rituximab per 50 mL.

Each carton and medication vial will be labelled with all the required information according to local regulations, including the Protocol Number (AGB 002) and a unique identifier (Med ID) in a blinded manner. This will be programmed into the Interactive Voice Telephone and Web Response System (IXRS). At each infusion visit, the IXRS will assign the carton for the allocated treatment group and visit and the Med ID will be linked to an individual patient. The Med ID is assigned by the IXRS.

Any used and unused product or waste material should be disposed of in accordance with local requirements when certificates of destruction are available, or if not possible, centrally as per Sponsor guidance. Further details will be documented in the Pharmacy Manual.

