4.13 Treatment Compliance

All doses of study drug will be administered in the clinic under the supervision of the Investigator or designee and recorded in the eCRFs. This should ensure full compliance.

The prescribed dosage, timing, and mode of administration of the study drugs described in this protocol may not be changed. Any departures from the intended regimen must be recorded in the eCRFs.

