$$\text{Dose (mL)} = [(\text{Patient BSA in m}^2) \times (375 \text{ mg/m}^2)] / 10 \text{ mg/mL (volume of rituximab).}$$

3. Study drug preparation should be done using aseptic techniques. Sterile, non-pyrogenic, disposable containers, syringes, needles, stopcocks, and transfer tubing, etc., should be used during dosage preparation and infusion.
4. Dilute the 2 vials of study drug (1000 mg) assigned via IXRS to a calculated concentration of 1 to 4 mg/mL rituximab in a 250, 500, or 1,000 mL infusion bag containing either 0.9% sodium chloride or 5% glucose for injection. Gently invert the bag to mix the solution. Discard any unused portion left in the vial. Inspect the vials for particulate matter and discoloration prior to administration.
5. Clearly label the bag with the study code, patient number and total dose of rituximab contained in the bag. Those used materials will be disposed in accordance with site practice.

Instructions for the i.v. Administration of Rituximab (same for both study drugs)

1. Do not administer as an i.v. push or bolus. Do not infuse the study drug concomitantly with another i.v. solution or other i.v. medications.
2. An infusion device capable of administering the study drug with rates varying from as low as 0.2 mL/minute up to 3.3 mL/minute would be suitable (eg, volumetric infusion pump). An in-line filter is not required.
3. Infusion of the study drug should be performed according to the recommended infusion rates provided in Table 1.
4. The first dose will be administered at an initial infusion rate of 50 mg/hour for the first hour. If no toxicity is seen, the rate may be increased gradually in 50 mg/hour increments at 30-minute intervals, to a maximum of 400 mg/hour.
5. If the first dose is well tolerated, the initial infusion rate for subsequent doses will be 100 mg/hour, increased gradually in 100 mg/hour increments at 30-minute intervals,

- to a maximum of 400 mg/hour. Patients who experienced infusion-related reactions to the first infusion should receive study drug as per the initial infusion schedule, with the rate of infusion not exceeding half that associated with the prior reactions. If this reduced rate is tolerated for 30 minutes, then the infusion rate may be increased to the next closest rate following the infusion schedule

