#### 4.8. PROTOCOL DEVIATIONS

Criteria defining protocol deviations are referenced in the Protocol Deviation Guidance and Protocol Deviation Specification. The Protocol Deviation specification will be developed according to the guidance and updated whenever a new version of the guidance is released. Additional updates before unblinding may be added in the case of protocol deviations which are not specified in the guidance but are reported from sites and classified as critical/major following assessment

All Critical/Major protocol deviations captured by programming or reported protocol deviations from sites, will be transferred to the biostatistics (BIOS) group by the project manager in IQVIA via email, will be summarized by category of deviation (e.g. Inclusion criteria) and treatment group using the RAN; and all protocol deviations, minor and major, will be listed (indicating which deviations are minor and which are major).

Protocol deviations do not lead to patient withdrawal unless they indicate a significant risk to the patient's safety. Protocol deviations leading to patient exclusion from the specific analysis sets (except for PK set and PD set) will be determined based on blinded data review prior to database lock.

---

Document:

Author:

Version Number:

Version Date:

Final v1.0

10Sep2019

Template No: CS\_TP\_BS016 Revision 4

Effective Date: 01Apr2016

Reference: CS\_WI\_BS005

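### The flat 1,000 mg overdose limit conflicts with uncapped 375 mg/m² dosing from a BSA of about 2.68 m² upward, and misses large overdoses at ordinary BSA (minor)

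*Protocol*

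**What the plan says.** Protocol Section 6.6 states that an overdose "is defined as an infusion of >1,000 mg during a single infusion in this study". Three things follow from the label. "Overdoses will be reported as protocol deviations"; the patient is to be monitored closely; and the case goes to the CRO's and sponsor's "medical advisors for decision on discontinuation of the patient". SAP Section 4.8 adds that "all protocol deviations, minor and major, will be listed". Only those graded critical or major are tabulated.

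The dosing rules are set elsewhere in the protocol:

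- Exclusion 7 in Section 3.2.2 removes "Patients with a body surface area" above 3.0 m², so 3.00 m² itself is eligible.
- Sections 4.1 and 4.7 set 375 mg/m² with no maximum dose. BSA is recalculated if weight changes by more than 10% before the next infusion.
- Section 4.13 says "The prescribed dosage, timing, and mode of administration of the study drugs described in this protocol may not be changed". Appendix 8 also rules out dose modification.
- Appendix 8 step 2 gives the volume as BSA × 375 / 10, rounded to three significant figures. The final rate step in its Table 1 is open-ended.
- Appendix 8 step 4 reads "Dilute the 2 vials of study drug (1000 mg) assigned via IXRS".
- Section 4.2 says "At each infusion visit, the IXRS will assign the carton for the allocated treatment group and visit" and leaves further details to the Pharmacy Manual.

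**The concern.** The overdose limit is a fixed number of milligrams, while the prescribed dose rises with BSA. At the top of the eligible BSA range the prescribed dose is larger than the limit, so a site cannot both follow the dosing rules and avoid the overdose label. The two-vial instruction makes this harder to read. It suggests a 1,000 mg ceiling, but no section states one.

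The same mismatch works in reverse for patients of ordinary size. Their dose is well below 1,000 mg, so a large excess can be given without meeting the definition.

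At stake is the accuracy of overdose and deviation reporting, a discontinuation discussion that a correctly dosed patient would not otherwise need, and clear preparation instructions for large patients. A patient in the band could be flagged at each of the four infusions.

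**Working it through.** The plan gives no derivation for the 1,000 mg limit, so there is no figure to reproduce. The check sets the limit against the dose rule.

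**Inputs.** Limit: above 1,000 mg (Section 6.6). Dose: 375 mg/m² (Sections 4.1 and 4.7). Largest eligible BSA: 3.00 m² (exclusion 7). BSA rounded to three significant figures (Section 4.7). Volume in mL rounded to three significant figures at 10 mg/mL (Appendix 8). Vial: 500 mg in 50 mL (Section 4.2).

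**Crossing point.** 1,000 / 375 = 2.667 m² before rounding.

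**With the protocol's rounding.** Volume = BSA × 37.5 mL; dose = rounded volume × 10 mg. The protocol does not say how halves are rounded, so both conventions are shown.

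| BSA (m²) | Unrounded dose (mg) | Volume (mL) | Dose, half-up (mg) | Dose, half-even (mg) |
|---|---|---|---|---|
| 2.66 | 997.5 | 99.75 | 998 | 998 |
| 2.67 | 1,001.25 | 100.125 | 1,000 | 1,000 |
| 2.68 | 1,005 | 100.5 | 1,010 | 1,000 |
| 2.69 | 1,008.75 | 100.875 | 1,010 | 1,010 |
| 2.80 | 1,050 | 105 | 1,050 | 1,050 |
| 2.90 | 1,087.5 | 108.75 | 1,090 | 1,090 |
| 3.00 | 1,125 | 112.5 | 1,130 | 1,120 |

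The conflict starts at 2.68 m² (half-up) or 2.69 m² (half-even). At 3.00 m² the correct dose is 12% to 13% over the limit.

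**After a weight gain.** Exclusion 7 applies at entry, but BSA can be recalculated later. By the SAP Section 9 formula, BSA is proportional to weight^0.425. A 10% gain multiplies BSA by 1.1^0.425 = 1.041, so 3.00 m² becomes about 3.12 m². The dose is then 3.12 × 37.5 = 117 mL, or 1,170 mg. So 1,125 mg is not a strict maximum.

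**Vials.** Two vials hold 2 × 500 = 1,000 mg. That is short of the calculated dose across the band. It is also not above 1,000 mg, so with two vials the definition cannot be met at any BSA.

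**The other direction.** At an assumed BSA of 1.70 m², the volume is 1.70 × 37.5 = 63.75, rounded to 63.8 mL, or 638 mg. If both vials were infused in full, the excess would be 1,000 / 638 − 1 = 57%, and Section 6.6 would not call it an overdose.

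**Who is in the band.** The SAP formula is BSA = 0.20247 × height^0.725 × weight^0.425. For BSA 2.68 to 3.00 m², at three illustrative heights:

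- 1.75 m: 168 to 219 kg (BMI 55 to 72)
- 1.85 m: 153 to 199 kg (BMI 45 to 58)
- 1.95 m: 140 to 182 kg (BMI 37 to 48)

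The documents give no BSA distribution, so the number affected among 308 patients is unknown and may be zero.

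**The case against.** The strongest reply is that the overdose label is conditional. Section 6.6 is triggered by drug actually infused. Under Appendix 8 step 4 as written only 1,000 mg is prepared, so no correct infusion could exceed the limit, and the limit matches the stated supply. This stands in part: the label arises only if more than two vials are assigned, and the allocation rule and Pharmacy Manual are not among the documents. It does not remove the inconsistency. With two vials, the step 2 dose cannot be given in the band, and reducing it is forbidden. One rule or the other fails.

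A second reply is that the band is very small, and that the medical advisors would see at once that the dose was as calculated. This stands, and is why the point is minor. Exclusion 7 nevertheless admits these patients, and no section exempts a correctly calculated dose from the overdose definition.

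A reader might infer that such patients would be taken off treatment, or that large patients will be underdosed. The documents support neither. Section 6.6 calls for a discussion and does not require stopping. Underdosing would breach Section 4.13 and Appendix 8, and a third vial may already be provided for.

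**Conclusion.** This is a minor internal inconsistency, wrong as written. Section 6.6 and Appendix 8 step 4 imply a 1,000 mg ceiling. Eligibility and the uncapped dose rule require more than that from about 2.68 to 2.69 m², about 1,125 mg at 3.00 m², and more if BSA is recalculated upward. Either a correct dose is labelled an overdose or it cannot be prepared; which one depends on a vial rule the documents do not show. The definition also misses large overdoses at ordinary BSA. The 57% example rests on an assumed BSA of 1.70 m² and on both vials being infused in full by mistake.

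A reader might also infer a threat to the trial's results. There is none here. Nothing in the rule changes how response at Week 28 is assessed or analysed, and the rule is the same in both blinded arms. An overdose label does not by itself remove a patient from the per-protocol or PK set: those exclusions rest on blinded review of deviations judged to affect the outcome or the PK. The guidance that would grade the deviation is not supplied. The size of the band in patients rests on the SAP's BSA formula, since Section 4.7 names none.

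**What to change.** - **Section 6.6.** Define overdose as an infusion that exceeds the patient's calculated dose for that visit (375 mg/m² × current BSA, rounded as in Appendix 8) by more than a tolerance set by the sponsor. The tolerance should be wide enough for normal preparation variation, for example 10%. One that covers rounding alone would flag ordinary infusions: 0.5% of 800 mg is only 4 mg. At 10%, the limit at 1.70 m² would be 638 × 1.1 = about 702 mg, so the 1,000 mg example would be caught.
- **No higher fixed limit.** It would still miss overdoses at ordinary BSA, and could again catch a correct dose after BSA is recalculated.
- **Appendix 8 step 4.** Replace the reference to two vials and 1,000 mg with *the assigned vials*, and confirm that the IXRS assigns a third vial when the calculated dose exceeds 1,000 mg.
- **If a 1,000 mg cap was intended**, state it in Sections 4.1 and 4.7 instead of changing the vial rule, and use the capped dose as the reference in Section 6.6.

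The cost is one sentence in Section 6.6, a few words in Appendix 8 and one check of the IXRS rule. Design, sample size and analysis do not change.
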